13.2 Sample Size/Accrual Rate

The primary objective is to characterize the effect on pharmacokinetic parameters when capecitabine is dosed on actual versus ideal body weight results in obese patients with advanced solid tumors. A mean difference in the AUC and Cmax of at least 30% between the ideal body weight dosing versus the actual body with based dosing will be considered as a minimal important difference. Based on the results of several previous PK studies involving capecitabine, it is anticipated that the overall standard deviation for the difference between the two dosing strategies is at most 25% of the mean difference. The following table shows the required sample sizes to detect various mean differences in PK parameters between the two dosing strategies at the two-sided 0.025 (=0.05/2 - a Bonferroni adjustment for comparing both AUC and Cmax) significance level with 80%

power, assuming a standard deviation ranging from 20-30%.

with 0070	power ai me inc	biaca 0.025 sig	infleance level				
	Mean difference in PK parameters between the ideal versus actual weight based dosing strategy						
Standard	20%	25%	30%	35%	40%		
Deviation							
20%	13	9	7	6	6		
25%	18	13	10	8	7		
30%	24	17	13	10	9		

Table 13.1: *Required sample sizes to detect various mean differences in PK parameters with 80% power at the two-sided 0.025 significance level*

A sample size of n=10 patients is proposed for this study. With a sample size of 10 patients, a clinically important difference of 30% between the ideal and actual body weight based dosing will be detected with 82% power at the one-sided 0.025 (=0.05/2 - a Bonferroni adjustment for evaluating both AUC and Cmax) significance level, assuming an overall standard deviation of 25%. A mean difference of only 25% will be detected with 68% power. Patients will be evaluable for the primary endpoint if he or she completes cycle 1, capecitabine therapy without dose reduction or skipped doses. Any patient who does not meet these criteria will be replaced.

The anticipated accrual is 1-2 patients per month. Therefore, the study is expected to be completed within 6-12 months after first accrual.

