(http://www.fda.gov/Drugs/DevelopmentApprovalProcess/DevelopmentResources/DrugInter actionsLabeling/ucm093664.htm) capecitabine is a weak inhibitor of CYP2C9. Thus, based on the drug interaction table in Appendix C, no medications would be contraindicated.

2.4 Hypothesis: Our hypothesis is that use of full weight based chemotherapy dosing will be associated with a significantly higher AUC and Cmax. The results of this study will advance oncologists' understanding of the potential impact of using limited weight-based dosing for capecitabine and provide preliminary data to demonstrate the need evaluate the importance of weight-based dosing for other chemotherapy and targeted agents.

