13. STATISTICAL CONSIDERATIONS

13.1 Study Design/Endpoints

The primary endpoints are the PK parameters (AUC and Cmax) of capecitabine when dosed using actual versus ideal body weight. Secondary endpoints are response and progression-free survival.

A single arm study design will be used to characterize the effect on pharmacokinetic parameters of capecitabine, when dosed using actual versus ideal body weight. Ideal body with based dosing of capecitabine when be used for cycle 1 from day 1 to day 7 followed by an actual body weight based dosing from Day 9 to Day 15. There will be a wash-out period on Day 8.

PK parameters will be summarized in terms of number of observations, means, standard deviations, medians, and ranges, stratified by assessment time point. The noncompartmental method will be used to estimate PK parameters. AUC will be estimated using the Lagrange approximation method. A paired t-test will be used to compare the PK parameters between the full weight and limited weight based dosing. If the PK parameters are not normally distributed, then an appropriate transformation will be identified before conducting the comparison. The comparison of AUC and Cmax between full weight and limited based dosing will be also performed using a population pharmacokinetics analysis, based on a nonlinear mixed effects modeling approach.

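### Cheap improvement, not an error: Holm's step-down test in place of Bonferroni for AUC and Cmax would raise the chance of showing both effects by about 7 to 11 points, if their correlation is 0.9 to 0.5

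*Combined protocol and SAP*

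**What the plan says.** Section 13.1 names two primary endpoints: "The primary endpoints are the PK parameters (AUC and Cmax) of capecitabine" under the two dosing weights. On the test it says: "A paired t-test will be used to compare the PK parameters between the full weight and limited weight based dosing". It gives no significance level, no multiplicity rule, and no statement of whether one or both parameters must be significant.

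The level appears only in section 13.2, and twice. For Table 13.1 the 0.025 is explained as "a Bonferroni adjustment for comparing both AUC and Cmax"; in full, the table is introduced as calculated at "two-sided 0.025 (=0.05/2 - a Bonferroni adjustment for comparing both AUC and Cmax) significance level with 80" per cent power. The sentence justifying n=10 then uses a "one-sided 0.025 (=0.05/2 - a Bonferroni adjustment for evaluating both AUC and Cmax) significance level" and states 82% power for a 30% difference with an SD of 25%, and 68% for a 25% difference. No step-down procedure is described anywhere.

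Section 2.4 hypothesises that full-weight dosing "will be associated with a significantly higher AUC and Cmax". The documents give no correlation between the AUC and Cmax differences.

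**The concern.** Under plain Bonferroni, the second parameter faces 0.025 even when the first has already been shown. That is stricter than control of the 5% family-wise error requires. Holm's procedure compares the smaller p-value with 0.025 and, only if that is significant, the larger with 0.05. It controls the family-wise error without any assumption about correlation.

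With 10 patients, and a hypothesis that names both parameters, the chance of showing both is worth knowing. The plan reports power for one parameter at a time and none for the pair. What is at stake is power on the second parameter; the validity of the trial is not in question.

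**Working it through.** **Inputs.** From section 13.2: n=10; difference 30% (also 25%); SD of the paired difference 25%; 0.025 per endpoint, family level 0.05. From section 13.1: paired t-test, so 9 degrees of freedom. Assumed: the correlation rho between the AUC and Cmax differences (varied from 0 to 1), bivariate normality, and the same standardised effect for both parameters.

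**1. The plan's own figures.** The noncentrality is (difference/SD) × √n, and the two-sided 0.025 critical value on 9 df is 2.685.
- 30%: (30/25) × √10 = 3.795, power 84.2% (plan: 82%).
- 25%: (25/25) × √10 = 3.162, power 68.2% (plan: 68%).
- All 15 cells of Table 13.1 reproduce at two-sided 0.025, including n=10 for 30%/25%.
- At one-sided 0.025 the two powers would be 92.0% and 80.3%, and the 30%/25% cell would be 8.

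The plan's numbers therefore rest on two-sided tests. The stated 82% is about 2 points low, which does not matter here.

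**2. Where the two rules differ.** Bonferroni shows both effects when the larger p ≤ 0.025. Holm shows both when the smaller p ≤ 0.025 and the larger p ≤ 0.05. The gain is the probability that the smaller p ≤ 0.025 while the larger lies between 0.025 and 0.05. At least one effect is shown under either rule when the smaller p ≤ 0.025, so that chance is identical.

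**3. Size of the gain.** 200,000 simulated trials per row; 30% difference, SD 25%, two-sided.

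| rho | Both, Bonferroni | Both, Holm | Gain (points) | Per endpoint, Holm | At least one, either rule |
|---|---|---|---|---|---|
| 0 | 71.0% | 84.1% | 13.1 | 90.9% | 97.5% |
| 0.5 | 74.0% | 85.2% | 11.2 | 89.8% | 94.4% |
| 0.7 | 76.2% | 86.0% | 9.8 | 89.2% | 92.3% |
| 0.9 | 79.5% | 86.9% | 7.4 | 88.0% | 89.1% |
| 0.99 | 82.7% | 85.7% | 3.0 | 85.7% | 85.7% |
| 1 | 84.2% | 84.2% | 0 | 84.2% | 84.2% |

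Per-endpoint power under Bonferroni is 84.2% in every row. By symmetry the per-endpoint gain is half the joint gain: at rho 0.5, 84.2 + 11.2/2 = 89.8.

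At a 25% difference, the chance for both rises from 52% to 67% at rho 0.5 (14.3 points) and from 61% to 71% at rho 0.9 (10.3 points).

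**4. Error control.** With both nulls true, simulated family-wise error was at most 0.049 for rho from -0.9 to 1. With one null true, Holm's was 0.042 to 0.047.

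**5. Sensitivity to sidedness.** With one-sided tests and a family level of 0.05, the gain is 7.3 points at rho 0.5 and 4.7 at rho 0.9.

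**The case against.** **Bonferroni is valid, so this is a choice between two sound methods.** This stands as to validity. A reader might infer that the plan contains an error; it does not. Type I error is controlled and the sample-size table reproduces. But the choice is not neutral, because Holm rejects whenever Bonferroni does, and sometimes more.

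**The 0.025 is a sizing level, and the analysis section sets no rule.** This is partly right. Section 13.1 has no Bonferroni text to replace, so the rule must be added there. Section 13.2 nevertheless states the adjustment as being for the comparison of both parameters, and no other rule is given.

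**The chance of showing both fits neither success rule.** If both parameters had to be significant, each could be tested at an unadjusted 0.05, giving 86.2% to 89.2% for rho 0.5 to 0.9, slightly above Holm. If one is enough, Holm does not change that chance. A reader might infer from section 2.4 that both are required. It names both but sets no such rule, and nor does section 13.1. Holm is valid either way and is never worse than Bonferroni.

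**It is not free.** This stands. When the larger p lies between 0.025 and 0.05, which is exactly where Holm gains, the 97.5% interval for that parameter includes zero although Holm declares significance. In a pilot meant to characterise an effect, intervals matter, and Bonferroni's match its test.

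**The size depends on unsettled inputs.** This stands too. A reader might take 7 to 11 points as following from the plan's own assumptions; it also needs a correlation that the documents do not give. Section 13.2 further describes the SD as at most 25% of the mean difference. Taken literally, the standardised effect is at least 1/0.25 = 4, power is near 100% and Holm has nothing to add. The table and stated powers instead put the 25% on the same scale as the 30%, and the figures here follow them.

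**Conclusion.** The point holds as an optional efficiency gain. At n=10, a 30% difference, an SD of 25% and two-sided tests, Holm adds 7.4 to 11.2 points to the chance of showing both effects for correlations of 0.9 down to 0.5. Over correlations from 1 down to 0 the gain runs from nil to 13.1 points. It adds nothing to the chance of showing at least one effect. It costs no type I error and no patients, but it does cost the simple agreement between test and interval. The documents support neither the view that Bonferroni is wrong here nor the view that Holm costs nothing.

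**What to change.** - In section 13.2, replace the Bonferroni rule with Holm's.
- In section 13.1, add that the smaller of the two paired t-test p-values is tested at two-sided 0.025 and, if significant, the other at two-sided 0.05. Fix this before the data are analysed.
- In section 13.2, reconcile the one-sided 0.025 in the power sentence with the two-sided 0.025 of Table 13.1.
- State that the 97.5% intervals are descriptive and do not decide significance.

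The cost is a few sentences. Table 13.1 and n=10 stand, because Holm's first step stays at two-sided 0.025. If the sponsor gives power for showing both parameters, the assumed correlation should be stated with it.

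### Section 13.2 sets the level for each primary PK test at two-sided 0.025 in two places and one-sided 0.025 in a third, and the stated 82% power fits neither

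*Combined protocol and SAP*

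**What the plan says.** Section 13.1 names the primary test but gives no level or sidedness: "A paired t-test will be used to compare the PK parameters between the full weight and limited weight based dosing".

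Section 13.2 gives the level three times:

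- The text introducing the sample sizes puts it "at the two-sided 0.025 (=0.05/2 - a Bonferroni adjustment for comparing both AUC and Cmax) significance level".
- The caption of Table 13.1 agrees: "with 80% power at the two-sided 0.025 significance level".
- The power sentence for n=10, a 30% difference and an SD of 25% says that the difference "will be detected with 82% power at the one-sided 0.025" level, with the same 0.05/2 Bonferroni explanation.

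The next sentence continues the same scenario: "A mean difference of only 25% will be detected with 68% power".

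Two other statements bear on the point. The hypothesis in Section 2.4 is directional: "use of full weight based chemotherapy dosing will be associated with a significantly higher AUC and Cmax". And Section 13.2 describes the variability by saying that "the overall standard deviation for the difference between the two dosing strategies is at most 25% of the mean difference", while the table and the power sentence use an SD of 25% as a figure in its own right.

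**The concern.** Section 13.2 is the only place where the significance level of the primary tests appears, and it gives two different ones. A directional hypothesis is compatible with a one-sided test, so a reader cannot dismiss the one-sided wording on sight. With 9 degrees of freedom the two levels have different critical values. If the analyst settles the matter only after seeing the data, a borderline AUC or Cmax result could be called significant or not by choosing which sentence to follow. The power quoted for the chosen sample size also needs to belong to one stated rule, and 82% does not obviously belong to either.

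**Working it through.** **Inputs.** Paired t-test (Section 13.1). From Section 13.2: n = 10; mean differences of 30% and 25%; SD of the difference 25%, read as percentage points as Table 13.1 uses it; level 0.025 per endpoint, two-sided or one-sided; 80% power for the table.

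**Method.** Exact power from the non-central t distribution with n − 1 degrees of freedom and non-centrality (difference/SD) × √n. The critical value is the 1 − 0.025/2 quantile of t for the two-sided test and the 1 − 0.025 quantile for the one-sided test. With 9 df these are 2.685 and 2.262.

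**Step 1: reproduce Table 13.1.** This is the smallest n with at least 80% power. Each row runs over differences of 20, 25, 30, 35 and 40%.

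| SD | Plan | Two-sided 0.025 | One-sided 0.025 |
|---|---|---|---|
| 20% | 13, 9, 7, 6, 6 | 13, 9, 7, 6, 6 | 10, 8, 6, 5, 5 |
| 25% | 18, 13, 10, 8, 7 | 18, 13, 10, 8, 7 | 15, 10, 8, 7, 6 |
| 30% | 24, 17, 13, 10, 9 | 24, 17, 13, 10, 9 | 20, 14, 10, 8, 7 |

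Two-sided matches 15 of 15 cells; one-sided matches 0 of 15.

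**Step 2: reproduce the power statements at n = 10, SD 25 points.**

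| Difference | Non-centrality | Two-sided 0.025 | One-sided 0.025 | Plan |
|---|---|---|---|---|
| 30% | (30/25) × √10 = 3.795 | 84.2% | 92.0% | 82% |
| 25% | (25/25) × √10 = 3.162 | 68.2% | 80.3% | 68% |

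The 68% is the two-sided value. The 82% is 2.2 points below the two-sided value and 10.0 points below the one-sided value. A simulation of 1,000,000 runs gave 84.3% and 92.1% for the 30% case.

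**Step 3: look for another source of the 82%.** At two-sided 0.025, n = 9 gives 78.1% and n = 11 gives 88.8%. The normal approximation at n = 10 gives 94.0%. Scaling n by 0.955, the usual efficiency adjustment for a Wilcoxon test, gives 81.7% for the 30% difference but 65.1% for the 25% difference, and it is not the planned test. None of these yields 82% and 68% together.

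**Step 4: what the two rules mean for a result.** The smallest significant mean difference is critical t × SD/√10, using the observed SD:

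| Observed SD | One-sided 0.025 | Two-sided 0.025 |
|---|---|---|
| 20 points | 2.262 × 6.325 = 14.3 | 2.685 × 6.325 = 17.0 |
| 25 points | 2.262 × 7.906 = 17.9 | 2.685 × 7.906 = 21.2 |
| 30 points | 2.262 × 9.487 = 21.5 | 2.685 × 9.487 = 25.5 |

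The chance, per endpoint, of a result on which the rules disagree is one-sided power minus two-sided power (true SD 25 points):

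- true difference 20%: 61.6% − 47.5% = 14.1%
- true difference 25%: 80.3% − 68.2% ≈ 12.2%
- true difference 30%: 92.0% − 84.2% = 7.8%
- true difference 35%: 97.5% − 93.7% = 3.8%

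**Step 5: the SD wording.** Read literally, 25% of a 30% mean difference is 0.25 × 30 = 7.5 points. The ratio of difference to SD would then be 4. Power at n = 10 would be practically 100%, and 4 patients would already give 97.9% at two-sided 0.025. The table's 10 patients therefore come from an SD of 25 percentage points.

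**The case against.** The strongest reply is that this is one wrong word and one slightly wrong number. The introductory text, the table caption, every table cell and the 68% all fit two-sided 0.025, and a directional hypothesis does not require a one-sided test. The 82% understates the two-sided power by only about 2 points, on the cautious side. The study is a 10-patient pilot whose aim is to characterise the PK effect. The t-test stands beside descriptive summaries and a population PK analysis, and no decision rule in the protocol depends on its p-value. Type I error is also 0.025 per endpoint under either rule taken alone; only the upper-tail share differs, 0.025 against 0.0125.

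Most of this stands, and it limits the weight of the point. Two-sided is the better-supported reading, the sample size is unaffected, and the disagreement probability is below 8% once the true difference exceeds the 30% that the plan treats as minimally important.

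What remains is that the only statement of the primary threshold contradicts itself. The error rate is held only if one rule is fixed in advance. An analyst free to use the one-sided cut-off for an increase and the two-sided cut-off for a decrease would work at 0.025 + 0.0125 = 0.0375 per endpoint.

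**Conclusion.** The concern holds. Section 13.2 contradicts itself on sidedness, nothing elsewhere resolves it, and the stated 82% is wrong under both readings: 84.2% two-sided, 92.0% one-sided. The calculations behind the table and the 68% were evidently done at two-sided 0.025, so the one-sided wording is most likely a slip, but the sponsor has to confirm that.

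The practical effect is modest. It is confined to results with t between 2.262 and 2.685, which is a mean difference of about 17.9 to 21.2 points if the observed SD is 25 points. At n=10 the power for the 30% target exceeds 80% either way. These figures assume approximately normal within-patient percent differences and a true SD of 25 percentage points. The critical values and the wording conflict do not depend on the SD. The description of the SD as a share of the mean difference is a separate wording error that affects neither the threshold nor n.

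**What to change.** - The sponsor confirms the intended sidedness before the PK data are analysed, taking the directional hypothesis in Section 2.4 into account, and states level and sidedness identically in Sections 13.1 and 13.2.
- If two-sided 0.025 per endpoint is confirmed, change the one-sided wording in the power sentence and restate power as 84% for a 30% difference. The 68% for a 25% difference and Table 13.1 stay as they are.
- If one-sided 0.025 is intended, change the introductory text and the table caption, restate power as 92% and 80%, and replace all 15 cells of Table 13.1 (for example, 8 instead of 10 at a 30% difference and SD 25%).
- In either case, describe the SD as that of the within-patient percent difference, at most 25 percentage points.

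The cost is an edit to Sections 13.1 and 13.2, plus the table in the one-sided case. The sample size of 10 and all patient procedures stay the same.

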5. TREATMENT PLAN

5.1 Administration

• Capecitabine treatment will be administered on an **outpatient** basis with the exception that cycle 1 days 1 and 9 will be administered on the Clinical Research Unit for pharmacokinetic blood draws. No investigational or commercial agents or therapies other than those described below may be administered with the intent to treat the patient's malignancy.

- The minimum number of hours between capecitabine doses should be 10 hours.
- Subjects should then be instructed to take the capecitabine dose 30 minutes after eating a normal meal.

• Subjects will be provided with a Medication Diary for capecitabine, instructed in its use, and asked to bring the diary with them to each appointment. Subjects will be instructed on what to do if missed, skipped, or vomited dose, and how to record this information. Please see Appendix B for the medication diary template.

Capectabile Doslig								
	Cycle 1							
	Day 1	Days 2-7	Day 8	Day 9	Days 10-15	Day 16-		
	_	-	-	-	_	21		
Capecitabin e Dose*	(1,250mg/ m ² twice daily)	(1,250mg/ m ² twice daily)	none	(1,250mg/ m ² twice daily)	(1,250mg/ m ² twice daily)	none		
Weight	Ideal Body	Ideal Body	n/a	Actual	Actual	n/a		
Used for	Weight	Weight		Body	Body			
BSA				Weight	Weight			

Capeci	tabi	ine	Dosing
	-		-

* The final dose will be rounded to nearest 150mg due to available pill sizes.

Cycle 2 and beyond: Capecitabine 1,250mg/m² orally twice daily days 1-14 of a 21 day cycle, using actual body weight.

The Mosteller calculation and the patient's ideal or actual body weight will be used to calculate the BSA³ (calculations below).

Mosteller BSA formula: BSA (m²) = ([Height(cm) x Weight(kg)]/ 3600)^{1/2}

Ideal Body Weight (men) = 50 + 2.3 (Height in inches - 60) Ideal Body Weight (women) = 45.5 + 2.3 (Height in inches - 60)

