5.5 Criteria for Removal from Study

Patients will be removed from study when any of the criteria listed in Section 5.3 applies. The reason for study removal and the date the patient was removed must be documented in the Case Report Form.

5.6 **Definition of Evaluable Patients**

Patients will be evaluable for the primary endpoint if he or she takes 100% of their capecitabine dose days 1 through 9 and at least 90% of their capecitabine dose days 10 through 15 in cycle one. Unevaluable patients will go off study after cycle 1, but may continue to be treated with commercial capecitabine per the discretion of the treating physician.

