6. DOSING DELAYS/DOSE MODIFICATIONS

6.1 General Guidance for Dose Reductions and Modifications

Additional cycles of therapy may be administered provided that the patient meets the following criteria on Day 1 of each cycle:

- ANC \geq 1,000/mcL
- Platelets \geq 75,000/mcL
- Non-hematologic toxicity recovered to \leq grade 1
- No evidence of progressive disease

Dose Modifications: Dose modification for toxicity will be based on the worst toxicity observed during the previous course. Dose modifications apply only when the event(s) are felt to be probably or definitely attributable to the study drugs. After recovery, dose adjustments for toxicity should be applied as below. Patients will be instructed to call with any new or worsening symptoms between clinical evaluations. Held doses will not be made up. All dose modifications will be permanent and continue through subsequent cycles.

Toxicities which are manageable with supportive therapy (ie. antiemetics or anti-diarrhea agents unless occurring despite maximal medical management.) do not require dose reductions. Toxicities which are determined to be clinically insignificant (ie. Lymphopenia) do not require dose reductions.

If an adverse event is not covered in section 6.2, doses may be reduced or held at the discretion of the investigator for the subject's safety.

	Initial Dose	1 st reduction	2 nd reduction
Capecitabine	$1,250 \text{ mg/m}^2$ orally	1,000mg/m ² orally	750mg/m ² orally
	twice daily	twice daily	twice daily

Table 3.	Capecita	abine Dos	e Levels

Dose delays for more than 2 weeks or subjects requiring more than 2 dose reductions will be removed from the study.

6.2 **Dose modifications**

All adverse events will be graded using the NCI Common Terminology Criteria for Adverse Events v4.0.

Hematologic toxicity (Neutropenia, Anemia, Thrombocytopenia): No dose modification for grade 1-2 toxicities. For Grade 3 hematologic toxicity, hold dose until \leq grade 1 or baseline. The may resume capecitabine with dose reduced to the next lower dose level. For grade 4 hematologic toxicity, the patient should discontinue drug and be removed from study. Consider testing for DPD deficiency.

Stomatitis/pharyngitis and other GI toxicities (excluding diarrhea, nausea and

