Grade 2: Painful erythema and swelling of the hands or feet and/or discomfort affecting the patient's normal activities	1 st occurrence	Institute supportive measures and hold capecitabine until toxicity resolves to Grade 1 or less. Institute at full dose when restarting therapy.
	2 nd or 3 rd occurrence	Continue supportive measures and hold capecitabine until toxicity resolves to Grade 1 or less. Upon resuming capecitabine treatment, decrease capecitabine to next lower dose level
	4 th occurrence	Off study
Grade 3: Moist desquamation, ulceration, blistering or severe pain of the hands or feet, or severe discomfort that causes the patient to be unable to work or perform activities of daily living	1 st occurrence	Institute supportive measures and hold capecitabine treatment for a minimum of 7 days and until toxicity has resolved to Grade 1 or less. When resuming treatment after dose interruption, resume capecitabine at next lower dose level
IIVINg	2 nd occurrence	Institute supportive measures and interrupt capecitabine treatment for a minimum of 7 days and until toxicity has resolved to Grade 1 or less. When resuming treatment after dose interruption, resume capecitabine at next lower dose level
	3 rd occurrence	Off study

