9. CORRELATIVE/SPECIAL STUDIES

9.1 Laboratory Correlative Studies

Capecitabine pharmacokinetics: Plasma samples for the analysis of capecitabine and metabolites (5-FU, DFCR, and DFUR) will be obtained at baseline (prior to dosing) and 1, 2, 3, 4, 6, and 8 hours after administration on day 1 and day 9 of cycle 1 and at steady state on cycle 1 days 7 and 15. Plasma and tissue concentrations will be measured by HPLC as previously described.³⁸. For 5FU, the standard curve is linear from 0.019 to 20 μ g/ml, r2 = 0.999, with an intraday variability ranging from 4.49%-5.52% over the standard curve. Inter-day variability over 2 weeks ranges from 4.33-5.42% over the standard curve and the lower limit of quantitation (LLOQ) is 0.0195 μ g/ml. For capecitabine, the standard curve is linear from 0.019 to 20 μ g/ml, r2 = 0.999, with intraday variability ranging from 1.2-7.8% and inter-day variability from 7.6-13.9% over 3 months and a LLOQ of 0.019 μ g/ml. The standard curves for DFCR and DFUR are both linear from 0.625 to 40 μ g/ml, r2 = 0.999, with an intraday variability over 4 weeks ranging from 3.45%-6.36% and 4.24-6.45% and LLOQ of 0.312 μ g/ml and 0.0195 μ g/ml, respectively.

Pharmacokinetic variables will be determined by noncompartmental methods with WinNonlin Pro version 5.2 (Pharsight Corporation, Cary, N.C.). Area under the plasma concentration–time curve is estimated using the trapezoidal rule from time 0 to peak concentration and the log-trapezoidal rule from the peak concentration to the last measurable plasma concentration (AUClast). AUC($0-\infty$) is then calculated from the time of dosing and extrapolated to infinity.

9.2 **PK Sample Collection**

Blood samples are collected in 6-mL EDTA (purple top) tubes at the timepoints described in Table 5, below on day 1, 7, 9 and 15 of cycle 1. Samples are then centrifuged at 3500RPM at 4°C to obtain plasma, aliquotted into cryovials and stored at -70C until analysis.

Time	Time
C1D1	C1D9
0 (prior to first capecitabine dose)	0 (prior to AM capecitabine dose)
1 hr post capecitabine dose	1 hr post capecitabine
2 hr post	2 hr post
3 hr post	3 hr post
4 hr post	4 hr post
6 hr post	6 hr post
8 hr post	8 hr post
C1D7	C1D15
0 (prior to AM dose of capecitabine)	0 (prior to AM capecitabine dose)

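### Evaluability for the primary endpoint is defined in two conflicting ways, and both definitions can discard a complete Day 1/Day 9 PK pair because of doses due after the last sample that can give AUC or Cmax

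*Combined protocol and SAP*

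**What the plan says.** Three places define who is evaluable for the primary endpoint.

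- Section 5.6, repeated in Section 11.1.1: the patient "takes 100% of their capecitabine dose days 1 through 9 and at least 90% of their capecitabine dose days 10 through 15" of cycle 1. Under 5.6 (and 5.3), an unevaluable patient leaves the study after cycle 1.
- Section 13.2: "Patients will be evaluable for the primary endpoint if he or she completes cycle 1, capecitabine therapy without dose reduction or skipped doses". It continues: "Any patient who does not meet these criteria will be replaced".

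The primary endpoints are AUC and Cmax (Section 13.1), and "A paired t-test will be used to compare the PK parameters between the full weight and limited weight based dosing". Section 13.1 adds a population PK analysis of the same comparison. Section 9.1 takes serial samples up to "6, and 8 hours after administration on day 1 and day 9 of cycle 1". The table in Section 9.2 gives Days 7 and 15 one pre-dose sample each. On dosing, Section 5.1 states: "The minimum number of hours between capecitabine doses should be 10 hours". Section 6.1 states: "Held doses will not be made up".

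**The concern.** The definitions cannot both apply. One tolerates a missed dose on Days 10-15 and the other tolerates none. Section 13.2 also rules out dose reductions, on which 5.6 and 11.1.1 are silent. The choice decides who enters the primary analysis, who is replaced and, through 5.3 and 5.6, who stays on study. In a trial of 10 patients, one or two classifications matter.

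Both definitions also set conditions on doses that cannot affect the primary data. Once the 8-hour sample on Day 9 has been drawn, the patient's contribution to the paired t-test is fixed. A dose missed or held after that changes neither profile, yet it can remove the pair. Those later doses are actual-weight doses, so removal depends on what happens under one of the two regimens being compared.

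**Working it through.** **The plan's own figure.** For a paired t-test with difference 30%, SD 25% and two-sided alpha 0.025, power comes from the noncentral t with n - 1 df and noncentrality (30/25) x sqrt(n). This gives 78.1% at n = 9 and 84.2% at n = 10, so the n = 10 of Table 13.1 reproduces. (The 82% in the text of 13.2 does not reproduce exactly. That is a separate matter.) The target is therefore 10 complete pairs, kept up by replacement.

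**Dose count in cycle 1 (Schema, Section 5.1).** Days 1-7: 7 x 2 = 14. Day 9: 2. Days 10-15: 6 x 2 = 12. Total 28. The last serial sample is 8 hours after the Day 9 morning dose and the next dose is at least 10 hours after it. The Day 9 evening dose and all of Days 10-15 therefore come later: 1 + 12 = 13 doses. The first 15 doses run through the Day 9 morning dose.

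**The two rules side by side, for a patient who took all 15:**

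| Later event | 5.6 / 11.1.1 | 13.2 |
|---|---|---|
| No dose missed | evaluable | evaluable |
| One missed on Days 10-15 (11/12 = 91.7%) | evaluable | replaced |
| Two missed on Days 10-15 (10/12 = 83.3%) | not evaluable | replaced |
| Day 9 evening dose missed | not evaluable | replaced |

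In every row the Day 1/Day 9 pair can be complete. The table counts a held dose as skipped under 13.2, which that section does not spell out.

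**Size.** The documents give no miss rate, so I assume p = 1%, 2% and 5% per dose. Let r be the within-patient correlation of misses. The group is patients who took all 15 doses through Day 9 morning.

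- r = 0: P(13.2) = (1-p)^13 and P(5.6) = (1-p)^13 + 12p(1-p)^12. At p = 2%: 0.769 and 0.769 + 0.188 = 0.957.
- r > 0: beta-binomial with a = p(1/r - 1) and b = (1-p)(1/r - 1). Fifteen doses already taken update b to b' = b + 15. With B the beta function, P(13.2) = B(a, b'+13)/B(a, b') and P(5.6) = P(13.2) + 12 B(a+1, b'+12)/B(a, b'). At p = 2%, r = 0.3: a = 0.0467, b' = 17.287, P(13.2) = 0.974, P(5.6) = 0.974 + 0.019 = 0.992 (from unrounded terms).

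Patients needed for 10 evaluable = 10/P. Share classified differently = P(5.6) - P(13.2). Entries are for p = 1% / 2% / 5%:

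| r | Needed, 13.2 | Needed, 5.6 | Classified differently |
|---|---|---|---|
| 0 | 11.4 / 13.0 / 19.5 | 10.2 / 10.4 / 11.9 | 11 / 19 / 32% |
| 0.1 | 10.4 / 10.8 / 12.2 | 10.1 / 10.2 / 10.6 | 2.9 / 5.6 / 12.4% |
| 0.3 | 10.1 / 10.3 / 10.7 | 10.0 / 10.1 / 10.2 | 0.9 / 1.9 / 4.5% |

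These are losses from later doses only. Patients lost before the Day 9 profile come on top, under any rule that requires the earlier doses.

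**The Day 15 sample.** A single pre-dose value gives neither AUC nor Cmax. Section 2.3 gives a half-life of about 0.75 h and a Tmax of 1.5 h, or 3 h with food. Assuming simple exponential decline, the fraction of peak left 10 hours after a dose is 0.5^((10-1.5)/0.75) = 0.04% to 0.5^((10-3)/0.75) = 0.16%.

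**The case against.** The strongest defence is that later adherence has a purpose. Section 9.1 plans a steady-state sample on Day 15, Section 13.1 plans a population PK analysis, and 10 of the 12 Day 10-15 doses precede that sample. This stands to the extent that an adherence condition can be justified for use of the Day 15 sample. It does not justify removing a complete pair from the t-test, which uses no Day 15 data, and the sample carries little information.

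It is also fair to say that 5.6 and 11.1.1 do little harm on their own. At r = 0.3 they cost at most 0.2 of a patient through later doses. The over-reach lies mainly in 13.2, and even there it is small if misses cluster within patients.

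Four stronger readings are tempting, and the documents do not support them:

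- **Loss of power.** Patients who fail are replaced, so 10 pairs remain.
- **Demonstrated bias.** Selection on tolerance of actual-weight dosing is possible, but nothing in the documents lets it be sized.
- **Hand-foot holds defeating both rules.** Table 4 says to "hold capecitabine treatment for a minimum of 7 days" after a first Grade 3 reaction, which from almost any point after the Day 9 profile would fail both definitions. But Section 8.1 puts hand-foot onset at a median of 79 days, range 11 to 360, so Days 9-15 lie before or at the very edge of that range. The 7-day minimum also does not apply to holds for other toxicities.
- **A distorted response rate.** Sections 13.4 and 13.5.2 keep all eligible patients in that analysis. At most, leaving after cycle 1 may reduce the assessments obtained at 6-9 weeks.

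**Conclusion.** The concern holds, as something that should be fixed. The conflict between 5.6/11.1.1 and 13.2 is textual and needs no assumption: one missed dose on Days 10-15 gives opposite classifications, and no section takes precedence. That both rules reach past the primary data follows from the sampling times and the dose interval alone.

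The size is less certain because it rests on assumed miss rates and exchangeable doses. Under 13.2, replacing losses caused by later doses takes 0.1 to 0.7 extra patients at r = 0.3, 0.4 to 2.2 at r = 0.1, and 1.4 to 9.5 if misses are independent. At the planned 1-2 patients per month, the r = 0.3 case adds at most 0.7 month. The firm consequences are an ambiguous primary analysis set and off-study status, and valid pairs discarded from a 10-patient pilot.

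**What to change.** Use one definition of the AUC/Cmax comparison set, under its own name, in Sections 5.6, 11.1.1 and 13.2: patients with the assigned dosing for the two profiles, and with Day 1 and Day 9 profiles that both allow AUC and Cmax to be computed. Set no condition on doses after the Day 9 morning dose. State which doses between the two profiles are required, and why. Section 2.3 reports that capecitabine PK was stable over time while 5-FU AUC was 34% higher on day 14 than on day 1, so the answer may differ by analyte.

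Replace only patients who fail this definition. Report the fully adherent subset as a sensitivity analysis. Apply any Day 10-15 adherence condition only to use of the Day 15 sample.

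Sections 5.3 and 5.6 tie unevaluable status to leaving the study. The sponsor must reconcile that wording with the new definition; no clinical rule is proposed here.

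The cost is protocol wording. There are no new samples, visits or procedures, and no more replacements than under 13.2.
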